11.4 Safety Assessments

Adverse events will be recorded when they are reported or observed. The AE collection period will begin at the time the subject is initially screened and continue for 15 days after the subject's last administration of study medication. Only the PI will determine the relationship to study medication for each AE prior to breaking the blind. The information will be recorded on the appropriate study center CRF and outpatient diary. In addition, vital signs (DBP, SBP, HR) will be assessed at the beginning and end of each 60 minute test session.

11.5 Blood Sampling, ECG and Pulse Oximetry

A blood sample (7 mL) will be taken at screening for purposes of assessing normal values for the subjects. Additional blood samples (7 mL each) will be taken at the beginning and end of each 60 minute test session to assess for the possible occurrence of subclinical methemoglobinemia. An ECG also will be performed both at Baseline and after the 60 minute sessions. All blood test analyses will be performed by the laboratory at Hospital of University of Pennsylvania-Pepper Lab. During each test session, subjects will also be monitored using pulse oximetry at Baseline and at 10, 20, 30, 40, 50 and 60 minutes. Methemoglobinemia is being defined as >5% of a subject's hemoglobin is in the methemoglobin state or a pulse oximetry reading is below 91%. The 5% level is still below the threshold where any clinically observable signs (blue lips,

chocolate-brown blood color or shortness of breath) would be seen. The study will be discontinued if a pulse oximetry reading falls below 91% or if the level of methemoglobinemia reaches > 5% in any subject.

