11.7 Study Participant Discontinuation

A subject will be considered discontinued from the study at any time under the following circumstances and will be replaced:

- a. Any subject who violates any condition of the entrance criteria after having been entered into the study;
- b. Any subject who develops a confounding concomitant illness (as determined by the subject, research coordinator or Investigator), serious adverse event, or a hypersensitivity to the study medication;
- c. Any subject who becomes uncooperative, does not adhere to the requirements of the study protocol, or refuses to complete the study;
- d. Any subject who requires any concomitant medication during the course of the study that could confound the study results;
- e. Any subject who for the last 2 of the 3 assessments has PPT scores of less than "3" and does not have at least 1 assessment of "4" or greater, or has a QST mean heat sensation assessment higher than 48.5°C based on the last 2 of the 3 assessments at Baseline prior to the start of each Session.
- f. Any subject who has a methemoglobinemia (>5%) or a pulse oximetry reading below 91% during Session 1 or Session 2.

If necessary, additional coded study medication will be provided to the study site for replacement subjects. A representative of Cetylite will provide the replacement number to the study site.

Subjects who discontinue due to an adverse event will not be replaced. All discontinued subjects will record no further assessments after their time of discontinuation, and any recorded efficacy data will be included in the intent-to-treat (ITT) efficacy analysis but not in the evaluable subject analysis. All subjects taking study medication with follow-up safety data will be included in the safety analysis. Details of the reason(s) why a subject has been discontinued from the study should be recorded in the appropriate section of the CRF.

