12. SAFETY

12.1 Subject Examinations

To ensure the safety and well-being of each subject entered into the study, the subject must first be examined by the PI or Sub-Investigator and medically cleared to participate as required by the protocol. Each subject will be observed for adverse events (AEs) and will be required to report any adverse events that develop during the course of the study and for 15 days post-drug treatment. If at any time during the study, the subject has a serious adverse event (SAE) or abnormality, the subject must be withdrawn from the study and appropriate care should be initiated.

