12.4.6 Discontinuation of Study due to an SAE

The study will be discontinued for safety reasons if a serious adverse event occurs in one subject unless it is demonstrated that the serious adverse event is not related (as defined in section 12.4.1 of this protocol) to study drug, in which case the study will not be required to stop.

The IRB will be notified within 24 hours of any event that results in discontinuation of the study.

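### The oximetry and methemoglobin trigger stops the whole study in Section 11.5, but in Section 11.7(f) and the flow chart it only removes a subject, whom 11.7 then says to replace

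*Combined protocol and SAP*

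**What the plan says.** Four places in the protocol give the consequence of a low oximetry reading, a high methemoglobin level, or both.

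- **Section 11.5** closes with a study-level rule: "The study will be discontinued if a pulse oximetry reading falls below 91% or if the level of methemoglobinemia reaches" more than 5% in any subject.
- **Section 11.7, lead-in**: "A subject will be considered discontinued from the study at any time under the following circumstances and will be replaced". Item (f) of the list below it reads "Any subject who has a methemoglobinemia (>5%) or a pulse oximetry reading below 91% during Session 1 or Session 2". The section then allows for extra coded medication, and a sponsor representative "will provide the replacement number to the study site".
- **Section 11.7, last paragraph**: "Subjects who discontinue due to an adverse event will not be replaced".
- **Section 4, flow chart footnote** on the 10- to 50-minute oximetry readings: below 91%, the subject is discontinued. The footnote does not mention stopping the study.

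The synopsis defines methemoglobinemia by the same two thresholds but attaches no study-level stop to them.

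On SAEs, item (b) of the same replaced list includes "serious adverse event, or a hypersensitivity to the study medication". Section 12.1 requires withdrawal in any case: "the subject must be withdrawn from the study and appropriate care should be initiated". Section 12.4.6 stops the study for one SAE unless it is shown to be not related, "in which case the study will not be required to stop".

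**The concern.** One clinical event carries different written consequences depending on the section read. Withdrawing the subject is compatible with stopping the study. Enrolling a replacement is not, because a stopped study enrols nobody. No sentence ranks the sections or provides for a pause or restart.

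This is a stopping rule in healthy volunteers, and the version table says version 6.0 was issued to bring in pulse oximetry and stopping rules. The site must act on it during a session. Staff working from the synopsis, the flow chart or 11.7 would not learn that dosing ends for everyone. The uncertainty also reaches the duty in 12.4.6 to tell the IRB within 24 hours of any event that results in discontinuation of the study.

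A second, smaller conflict sits inside 11.7. An SAE is a kind of adverse event, so such a subject is both replaced (item b) and not replaced (last paragraph).

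**Working it through.** The plan states no figure for this point, so the check is mainly a comparison of texts.

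**1. Is it the same trigger?** Yes. Sections 11.5 and 11.7(f) both use oximetry below 91% or methemoglobin above 5%. The footnote uses the oximetry limb only.

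**2. What follows from it?**

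| Place | Subject | Replacement | Study |
|---|---|---|---|
| 11.5 | not stated | not stated | stops |
| 11.7 lead-in with (f) | withdrawn | yes | not stated |
| 11.7 last paragraph, if classed as an adverse event | withdrawn | no | not stated |
| Flow chart footnote | withdrawn | not stated | not stated |

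The second row conflicts with the first and the third.

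**3. Could 11.5 mean only that the study ends for that subject?** The footnote makes this possible. Three things count against it: the sentence is about the study and is triggered by any subject; 12.4.6 uses parallel wording for a plain study-level stop; and version 6.0 was issued to add stopping rules. If the narrow meaning was intended, the last sentence of 11.5 needs rewording instead.

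**4. What depends on the choice?** Inputs: 76 subjects with two exposures each, so 76 × 2 = 152, which reproduces the synopsis figure.

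- If the first exposure triggers and 11.5 applies, further exposures = 0.
- If only that subject is withdrawn, the others still due are 76 − 1 = 75 subjects, or 75 × 2 = 150 exposures. A replacement adds 2, giving 152.
- If the last exposure triggers, no other planned exposure remains, so the only further dosing would be a replacement's 2 exposures.

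The range is therefore 0 to 150 planned exposures in other volunteers, depending on when the trigger occurs.

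**5. How likely is it to matter?** The documents give no trigger rate. As an assumption, let each exposure trigger independently with probability p. Then P(at least one trigger in 152) = 1 − (1 − p)^152, and the expected number is 152p.

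| Assumed p | P(at least one) | Expected number |
|---|---|---|
| 0.1% | 14% | 0.15 |
| 0.5% | 53% | 0.76 |
| 1% | 78% | 1.52 |
| 2% | 95% | 3.04 |

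Under 11.5 the middle column is the chance that the trial ends early. Under a subject-level rule the last column is roughly the number of subjects lost. The finding does not rest on any of these rates.

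**6. SAE replacement.** A related SAE stops the study under 12.4.6, so replacement arises only after an SAE shown to be not related. Section 9.1 plans 76 completed subjects. One such withdrawal leaves 76 if item (b) governs and 76 − 1 = 75 if the last paragraph governs.

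**The case against.** The strongest reply is that 11.7 already supplies its own exception. The no-replacement sentence follows the list and reads naturally as a limit on a general lead-in. The trigger would normally be an adverse event: Section 12.4.1 counts abnormal laboratory findings that are a change from baseline. Exclusion criterion (g) removes anyone below 96% at Baseline of either session, so a later reading below 91% is a fall of more than 96 − 91 = 5 points. On this view the text fits together: the subject is withdrawn, is not replaced, and the study stops under 11.5. Replacement is not automatic either, since the sponsor must issue a number.

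Much of this stands, and it is probably what was meant. It does not make the text correct. On that reading the lead-in is wrong for item (f) and for SAEs in item (b), and the last paragraph does not present itself as an exception to them. It also leaves the footnote with a subject-level consequence only, and does not cover a trigger that is not classed as an adverse event, such as methemoglobin already above 5% in the pre-dose sample.

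A reader might infer more than the documents support:

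- *Item (f) orders the trial to carry on.* It does not. Section 11.7 governs participants and is silent on whether the study continues.
- *A replacement would be over-exposed.* From Table 2, the two-session totals are 28 + 28 = 56 mg benzocaine with 4 mg tetracaine HCl, or 56 + 28 = 84 mg with 8 mg. These are the planned doses for any participant, given 4 to 14 days apart, and each session stays within the 56 mg and 8 mg daily limits in 12.4.3.
- *An SAE subject might stay in.* Sections 11.7 and 12.1 both require withdrawal; only replacement is unclear.
- *The statistical conclusions are at risk.* Section 13.1 gives no power calculation that one subject could upset, and nothing here touches alpha or the primary analysis.

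**Conclusion.** Wrong as written, and should be fixed. The same trigger is a whole-study stop in 11.5, a withdrawal with replacement in 11.7(f), and a bare withdrawal in the flow chart footnote. The no-replacement sentence in 11.7 probably reflects the intent but contradicts the lead-in.

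The size is best put as whether any remaining volunteer is dosed after a trigger: none, or between 0 and 150 planned exposures in other subjects depending on timing. Counting only the one replacement subject would understate it. The SAE conflict is minor: 75 or 76 completers, and only after an SAE shown to be not related.

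The conclusion assumes that 11.5 is a study-level rule, which its wording favours. If it is not, the sections still disagree and 11.5 is the one to change. No event rate is needed.

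**What to change.** 1. Take item (f) out of the replaced list. State that the subject is withdrawn, is not replaced, and that all dosing stops under 11.5.
2. Align the flow chart footnote with this.
3. If only withdrawal of the subject is intended, amend the last sentence of 11.5 instead, with IRB approval, and say under (f) whether the subject is replaced.
4. Qualify the 11.7 lead-in along these lines: *and, unless the discontinuation is due to an adverse event, will be replaced*.
5. Cross-refer the SAE entry in item (b) to 12.4.6.

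The cost is a wording amendment with IRB approval, and no added procedures, subjects or visits. The downside of not replacing adverse-event withdrawals is at most one or a few fewer completers.

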11.6 Concomitant Medication

No other medications expected to confound the evaluation of the study medication will be allowed prior to or during the test sessions. This includes, but is not limited to, the use of any analgesics, oral rinses and mouth lozenges. All concomitant medications used during the study will be recorded in the CRF.

11.7 Study Participant Discontinuation

A subject will be considered discontinued from the study at any time under the following circumstances and will be replaced:

- a. Any subject who violates any condition of the entrance criteria after having been entered into the study;
- b. Any subject who develops a confounding concomitant illness (as determined by the subject, research coordinator or Investigator), serious adverse event, or a hypersensitivity to the study medication;
- c. Any subject who becomes uncooperative, does not adhere to the requirements of the study protocol, or refuses to complete the study;
- d. Any subject who requires any concomitant medication during the course of the study that could confound the study results;
- e. Any subject who for the last 2 of the 3 assessments has PPT scores of less than "3" and does not have at least 1 assessment of "4" or greater, or has a QST mean heat sensation assessment higher than 48.5°C based on the last 2 of the 3 assessments at Baseline prior to the start of each Session.
- f. Any subject who has a methemoglobinemia (>5%) or a pulse oximetry reading below 91% during Session 1 or Session 2.

If necessary, additional coded study medication will be provided to the study site for replacement subjects. A representative of Cetylite will provide the replacement number to the study site.

Subjects who discontinue due to an adverse event will not be replaced. All discontinued subjects will record no further assessments after their time of discontinuation, and any recorded efficacy data will be included in the intent-to-treat (ITT) efficacy analysis but not in the evaluable subject analysis. All subjects taking study medication with follow-up safety data will be included in the safety analysis. Details of the reason(s) why a subject has been discontinued from the study should be recorded in the appropriate section of the CRF.

12. SAFETY

12.1 Subject Examinations

To ensure the safety and well-being of each subject entered into the study, the subject must first be examined by the PI or Sub-Investigator and medically cleared to participate as required by the protocol. Each subject will be observed for adverse events (AEs) and will be required to report any adverse events that develop during the course of the study and for 15 days post-drug treatment. If at any time during the study, the subject has a serious adverse event (SAE) or abnormality, the subject must be withdrawn from the study and appropriate care should be initiated.

12.2 Subject Safety Information

In accordance with the regulatory requirements regarding informed consent (21 CFR Part 50 Protection of Human Subjects), the subject will receive a copy of the informed consent form when discharged from the clinic. The informed consent form will include the information needed to contact the PI, along with a description of the study medication the subject may have received.

12.3 Availability of Investigator

Either the PI or an appropriate designee will be available to the subject at all times during the study and names and phone numbers of the PI and/or appropriate designee will be listed on the informed consent form.

12.4 Adverse Events

12.4.1 Definitions

Adverse Event

An adverse event (AE) will be defined as any untoward medical occurrence in a subject administered study medication. The adverse event does not necessarily have to have causal relationship with the study medication. An AE can therefore be an unfavorable and unintended sign (including an abnormal laboratory finding), symptom, or disease, which is a change from baseline and is temporally associated with the use of the study medication, whether or not it is considered related to the study medication.

Severity

The following definitions will be used for grading severity of adverse events:

Mild - Either asymptomatic or subject is aware of the sign, symptom or event, but it is easily tolerated.

Moderate - Discomfort enough to cause interference with usual activity and may warrant intervention.

Severe - Incapacitating with inability to do usual activities.

Causal Assessment

The causal relationship between an AE and the study medication will be determined by the PI on the basis of his clinical judgment and the following definitions:

- Associated: There is a reasonable possibility that the AE may have been caused by the study medication. This definition applies to those AEs that are considered definitely, probably, and possibly related to the use of the study medication.
 - a. Definitely Related: An AE that: follows a reasonable temporal sequence from administration of the study medication; follows a known response pattern to the study medication; and, when appropriate to the protocol, is confirmed by improvement after stopping the study medication (positive de-challenge) and by reappearance of the reaction after repeat exposure (positive re-challenge); and cannot be reasonably explained by known characteristics of the subject's clinical state or by other therapies.
 - b. Probably Related: An AE that: follows a reasonable temporal sequence from administration of the study medication; follows a known response pattern to the study medication; and, when appropriate to the protocol, is confirmed by improvement after de-challenge; and cannot be reasonably explained by the known characteristics of the subject's clinical state or by other therapies.
 - c. Possibly Related: An AE that: follows a reasonable temporal sequence from administration of the study medication and follows a known response pattern to the study medication but could have been produced by the subject's clinical state or by other therapies.
- Not Associated:
 - a. Unlikely: An AE that does not follow a reasonable temporal relationship after administration of the study medication or could have been produced by the subject's clinical state or other therapies.
 - b. Not related: An AE for which sufficient information exists to indicate that the etiology is unrelated to the study medication. Two or more of the following variables apply:
 - The AE does not follow a reasonable temporal sequence after administration of the study medication;
 - The AE is readily explained by the subject's clinical state or other therapies;
 - Negative de-challenge—the AE does not abate upon dose reduction or cessation of therapy (assuming that it is reasonable to expect abatement of the AE within the observed interval).

Serious Adverse Event

A serious adverse event (SAE) is any untoward medical occurrence that occurs at any dose and:

- Results in death;
- Is life threatening;
- Requires inpatient hospitalization or prolongation of an existing hospitalization;
- Results in persistent or significant disability/incapacity;
- Is a congenital anomaly/birth defect.
- Is a medically important condition: Important medical events that may not result in death, be life-threatening, or require hospitalization may be considered a SAE when, based upon appropriate medical judgment, the event(s) may jeopardize the subject and may require medical or surgical intervention to prevent one of the outcomes listed in this definition.

12.4.2 Reporting Adverse Events

Any SAE, regardless of causal relationship, must be reported immediately to the Medical Monitor at Cetylite no later than 24-hours after awareness of the SAE. Initial SAE reports may be made by telephone, and then followed by faxing a completed "Serious Adverse Event Form" and confirming by telephone that the fax was received. Compliance with this time requirement is essential so that Cetylite may comply with its regulatory obligations.

Contact:

Medical Monitor:

Name:	[name]
Address:	[name]
[contact]
Fax:	Same

Follow up information relating to a serious adverse event must be reported to the Medical Monitor and to Cetylite within 24 hours of receipt by the PI by faxing a completed "Serious Adverse Event Form" to Cetylite and confirming by telephone that the fax was received. The subject will be observed and monitored carefully until the condition resolves or stabilizes and its cause is identified. The PI also will promptly notify the appropriate Institutional Review Board about the serious adverse event.

12.4.3 Other Reportable Events

The following events will be recorded and reported in the same time frame and following the same process as for serious adverse events:

- Overdose or abuse of the study medication with or without adverse events (for this protocol, a total daily dose of benzocaine exceeding 56 mg/day) or tetracaine exceeding 8 mg/day;
- Inadvertent or accidental exposure to the study medication with or without an adverse event.

12.4.4 Adverse Event Recording and Reporting

All AEs, whether serious or not, will be recorded on source documents and CRFs. The recording period for AEs and SAEs starts at the time the subject is screened. The recording period for both AEs and SAEs lasts through 15 days after the subject's last administration of study medication, regardless of the relationship to the study medication. The PI must follow up as medically necessary on all AEs, SAEs, and other reportable events until the event has subsided or values have returned to baseline, or in the case of permanent impairment, until the condition stabilizes.

For SAEs, the PI will provide all documentation pertaining to the event (*e.g.* additional laboratory tests, consultation reports, discharge summaries, postmortem reports, etc.) to the Cetylite Medical Monitor in a timely manner. Reports relative to the subject's course must be submitted to Cetylite until the event has subsided or, in the case of permanent impairment, until the condition stabilizes.

Information about all adverse events, serious and non-serious, including the event's severity, start and stop times/dates, chronicity, relatedness to study medication, and any actions taken, must be recorded on the appropriate CRFs. The information recorded will be based on the signs and symptoms detected during the physical examination and clinical evaluation of the subject as well as information recorded in the subject's diary, when applicable.

